2.9 Handling of Missing Data

[REDACTED]

2.10 Poolability Issue

2.10.1 Poolability Issue of the Randomized Cohort

Analysis will be performed pooling data across study sites.

[REDACTED]

[REDACTED]

2.10.2 Poolability Issue of the Single-Arm Cohort

[REDACTED]

2.11 Multiplicity Issues

Since the analysis population for the Randomized Cohort and Single-Arm Cohort are mutually exclusive, the primary and secondary endpoints for the Randomized Cohort and Single-Arm Cohort will be evaluated separately and need no multiplicity adjustment. Within each cohort, sequential testing will be performed for the pre-specified endpoints. Therefore, the overall type I error is under control.

Statistical Analysis Plan

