## TRILUMINATE Pivotal CIP (Version F)

A group sequential design with one interim analysis will be performed. The primary endpoint will be evaluated once the first 100 subjects have completed 12-month follow-up. If the primary endpoint is successfully met at the interim analysis, the Single-arm cohort endpoints will be summarized descriptively for all additional subjects enrolled after the first 100. If unsuccessfully met, the primary endpoint will be re-analyzed when all enrolled subjects in the Single-arm cohort have completed 12 months follow-up.

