1.3 Clinical Investigation Design

TRILUMINATE Pivotal trial is a prospective, multicenter, randomized, controlled, clinical trial of the TriClip™ device in symptomatic subjects with severe TR, who have been determined by the site's local heart team to be at intermediate or greater estimated risk of mortality or morbidity with tricuspid valve surgery.

The trial consists of two cohorts: Randomized cohort and Single-arm cohort. Determination as to whether a patient is placed in the Randomized cohort or Single-arm cohort will be made by the independent eligibility committee. Patients will be placed in the Single-arm cohort if they meet the following criteria:

- The likelihood of achieving TR reduction of at least 1 grade (as assessed using a 5-grade scale) is high, and
- The likelihood of achieving TR reduction to moderate or less (≤ 2) is low

All other patients will be randomized.

Randomization will occur in a minimum of 350 eligible subjects in a 1:1 ratio to receive either the TriClip™ device or medical therapy (control group), at up to 80 sites as follows:

- **TriClip™ Device (Device) Group:** Eligible subjects will undergo the TriClip procedure and will continue to be managed on medical therapy, per physician discretion.
- **Medical Therapy (Control) Group:** Eligible subjects will not undergo the TriClip procedure but will continue to be managed on medical therapy, per physician discretion.

The Single-arm cohort will enroll approximately 200 eligible subjects and all subjects will receive the TriClip™ device.

Statistical Analysis Plan

Additionally, up to 3 roll-in subjects will be permitted per implanter without prior experience of transcatheter treatment of the tricuspid valve. The trial will be conducted in US, Canada and Europe, with a minimum of 50% of the subjects in each cohort enrolled in the US.

Following the completion of enrollment of the TRILUMINATE Pivotal trial, subjects from eligible sites will be enrolled into a continued access study (CAS). Details of the analysis plan to continued access study is included in Appendix B.

An independent Clinical Events Committee (CEC) will adjudicate events including cause of death, HF hospitalization and components of major adverse events. The independent ECL will assess echocardiographic endpoints.

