2.3.2.2.2 Freedom from Major Adverse Events (MAE) at 30 Days Post Procedure

The freedom from MAE occurring after procedure attempt (femoral vein puncture) at 30 days is the secondary measure of safety for TriClip™ in the Single-Arm Cohort. The analysis of this secondary endpoint is a one-group test against an objective performance goal of 80%.

The null and alternative hypotheses are stated as:

$$H_0: P_{30D} \leq 80\%$$

$$H_1: P_{30D} > 80\%$$

where P_{30D} is the probability of freedom from any MAE at 30-day post procedure. A [REDACTED]

[REDACTED]

Statistical Analysis Plan

[REDACTED]

The null hypothesis will be rejected at a one-sided 2.5% level of significance.

2.3.2.2.3 Change in 6MWT (Six Minute Walk Test) Distance at 12 Months over Baseline

Improvement in the 6MWT distance at 12 months from baseline is an important secondary effectiveness endpoint.

The null and alternative hypotheses are stated as:

$$H_0: \mu_{\Delta 6MWD} \leq 0 \text{ vs.}$$

$$H_1: \mu_{\Delta 6MWD} > 0$$

where $\mu_{\Delta 6MWD}$ represents the mean change in 6MWT distance at 12 months from baseline.

The analysis will be performed in subjects with paired 6MWT data at baseline and 12 months. [REDACTED]

[REDACTED] Paired t test will be used to compare the mean change to 0 and the null hypothesis will be rejected at a one-sided 2.5% level of significance.

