2.4.2.2 Single-arm Cohort – Secondary Endpoints

The secondary endpoints of the Single-arm cohort will be evaluated only if the primary endpoint of the Single-arm cohort is met. Hence, the following secondary endpoints are adequately powered ($\geq 80\%$) with a sample size of 100 at the interim analysis for primary endpoint.

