2.6.2 Single-arm Cohort

If the primary endpoint of the Single-arm cohort is met at the interim analysis, the secondary endpoints of the Single-arm cohort will be evaluated for the same cohort as the primary endpoint. The Single-arm cohort endpoints of all additional subjects enrolled after the first 100 will be summarized descriptively. If the primary endpoint is not met at the interim analysis, then it will be re-analyzed when all enrolled subjects in the Single-Arm cohort complete 12 months follow-up.

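### Single-arm cohort: a fixed testing order does not by itself hold each secondary endpoint at one-sided 2.5% when the primary that opens the sequence has two looks

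*SAP*

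**What the plan says.** **Two looks at the primary.** Protocol 5.2.1: "A group sequential design with one interim analysis will be performed". The first look: "The primary endpoint will be evaluated once the first 100 subjects have completed 12-month follow-up". The second: "If unsuccessfully met, the primary endpoint will be re-analyzed when all enrolled subjects in the Single-arm cohort have completed 12 months follow-up". SAP 2.6.2 agrees: "If the primary endpoint is not met at the interim analysis, then it will be re-analyzed when all enrolled subjects" have reached 12 months. SAP 1.3 gives the size: "The Single-arm cohort will enroll approximately 200 eligible subjects and all subjects will receive the TriClip™ device"; the Protocol says up to 200.

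**When the secondaries are tested.** SAP 2.11.2 tests them in a fixed order, for labeling claims, if the Single-arm primary is met, and does not limit this to one look. SAP 1.4.2.2 assesses them at the same time as the primary. SAP 2.6.2 adds that, if the interim succeeds, they use the same cohort as the primary and later subjects are only described. Read together, the secondaries use the first 100 subjects after an interim success and all enrolled after a final success. The second half of that is inferred from 1.4.2.2 and 2.11.2; 2.6.2 does not spell it out.

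**At what level.** All five secondaries (SAP 2.3.2.2.1 to 2.3.2.2.5) carry one-sided 2.5%. The MAE endpoint, for example: "The null hypothesis will be rejected at a one-sided 2.5% level of significance". SAP 2.4.2.2 says they are adequately powered "with a sample size of 100 at the interim analysis for primary endpoint", and the power statements beneath it use the full 2.5% with about 100 subjects.

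**The claim of control.** SAP 2.11, after noting that the two cohorts do not overlap, concludes: "Within each cohort, sequential testing will be performed for the pre-specified endpoints. Therefore, the overall type I error is under control".

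**The concern.** A fixed sequence protects each endpoint when every test is run once on a data set that does not depend on the results. Here the data set for a secondary is chosen by the primary. A good run in the first 100 subjects passes the primary early and, if the endpoints are positively correlated, tends to favour the secondary on those same subjects. If the early run is poor, the secondary is tested later on more data. The probability of rejecting a true secondary null, summed over the two routes, can exceed 2.5%.

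Some positive correlation is built in: survival is part of the primary and of the 12-month survival and surgery secondary. The documents give no correlation for any pair of endpoints.

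At stake is the stated error rate of the Single-arm secondary labeling claims.

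**Working it through.** **1. The plan's own figure.** SAP 2.4.2.1 gives primary power of about 90% with 100 subjects and more than 95% overall with 200. The assumed response rate and the boundaries are redacted, so this can only be checked for consistency. With the 30% goal and an exact binomial test at n=100:

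- Interim level 2.5%: 40 or more responders needed; 90% power at a true rate of about 46%.
- Pocock interim level (0.0147): 41 or more; about 47%.
- Lan-DeMets O'Brien-Fleming interim level (0.0015): 45 or more; about 51%.

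Each gives overall power above 99% at 200. All are compatible with the stated figures, which therefore do not reveal the boundary.

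**2. Inputs for the secondary error.**

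- From the documents: two looks, 100 and about 200 subjects, secondary critical value 1.960 (one-sided 2.5%).
- Assumed: information fraction 100/200 = 0.5; primary boundary (c1, c2) = (2.797, 1.977) O'Brien-Fleming, (2.963, 1.969) Lan-DeMets O'Brien-Fleming or (2.178, 2.178) Pocock; joint normality; correlation ρ between primary and secondary varied.

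**3. Formula.** For a null secondary tested once, at the look where the primary first passes:

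error = P(Zp1 > c1, Zs1 > 1.960) + P(Zp1 ≤ c1, Zp2 > c2, Zs2 > 1.960)

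Within an endpoint the two looks correlate √0.5 = 0.707. The primary has mean θ√0.5 at look 1 and θ at look 2; the secondary has mean 0. The error is maximised over θ.

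Example, O'Brien-Fleming, ρ = 0.5: the maximum is near θ = 3.00, where the two terms are 1.779% + 1.075% ≈ 2.85%.

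| ρ | O'Brien-Fleming, worst case | Pocock, worst case | Either, at 90% interim power |
|---|---|---|---|
| 0 | 2.50% | 2.50% | 2.5% |
| 0.3 | 2.69% | 2.61% | 2.54% |
| 0.5 | 2.85% | 2.75% | 2.53% |
| 0.7 | 3.08% | 2.96% | 2.51% |

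The Lan-DeMets version differs from O'Brien-Fleming by about 0.01 point. At ρ = 0 the error is 2.5% × P(primary passes), so it cannot exceed 2.5%.

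**4. Where the worst case lies.** Interim power of the primary is Φ(θ√0.5 − c1). With O'Brien-Fleming and ρ = 0.5: Φ(3.00 × 0.707 − 2.797) = Φ(−0.676), about 25%. At ρ = 0.7 (θ near 2.34): Φ(1.655 − 2.797) = Φ(−1.142), about 13%. The maxima occur where the primary effect is well short of the one planned.

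**5. Check of the remedies.** If the secondary is always tested on the first 100 subjects, its error is at most P(Zs1 > 1.960) = 2.5%, whichever look the primary passes at. If it has a Pocock boundary of 2.178 at each look, the worst case is 2.49% (O'Brien-Fleming primary) or 2.50% (Pocock primary). The power cost at n=100 is Φ(z_power + 1.960 − 2.178):

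- 83%: Φ(0.954 − 0.218) = Φ(0.736), about 77%.
- 90%: Φ(1.282 − 0.218) = Φ(1.064), about 86%.

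**The case against.** **Redaction.** SAP 2.5.2 is blacked out and may set look-specific levels for the secondaries. The primary's own section also says only one-sided 2.5%, although the primary is known to be group sequential, so that wording cannot rule out spending described elsewhere. This stands: a reader might infer that the statement in 2.11 is simply false, and the documents do not support that. Nor does 2.11 say that ordering alone is enough. But a reduced interim level in 2.5.2 would conflict with the visible n=100 power figures. With an O'Brien-Fleming interim value of 2.797, for instance, a stated 83% becomes Φ(0.954 + 1.960 − 2.797) = Φ(0.117), about 55%. A clarification is needed either way.

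**One test, not two.** A reader might infer two chances at full alpha and quote the error of two ungated looks at 1.960, about 4.2%. The SAP describes no such procedure. After an interim success later subjects are only described, so each secondary is tested at most once.

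**Size.** At the planned 90% interim power the error is 2.50–2.54%. If the stated 90% refers to an unadjusted 2.5% level, it is 2.5–2.7%. This also stands, but type I error control should not depend on the assumed primary effect being true.

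**Other gates.** 6MWT, survival and HF hospitalization come third to fifth in the order, and a false claim on them also needs TR reduction and MAE to pass. The calculation ignores those gates, so it is an upper bound in that respect. The exact binomial test for TR reduction is conservative in itself (1.76% at n=100, 2.00% at n=200), which offsets part of any excess.

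**Conclusion.** The point holds as a gap in the stated justification. As visibly written, each Single-arm secondary is tested at most once at full one-sided 2.5%, on a data set selected by the primary, and fixed ordering does not guarantee 2.5% for a secondary positively correlated with it. The worst-case error runs from about 2.6% to 3.1% for correlations of 0.3 to 0.7. This rests on an information fraction of 0.5, a standard boundary, joint normality and correlations that the documents do not give.

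A reader might infer that the trial's conclusion is affected. It is not: SAP 2.7 ties trial success to the Randomized cohort primary. The excess is modest, but the claims are for labeling and the correction is cheap.

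**What to change.** In SAP 2.11.2, do one of the following:

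- **(a)** Prespecify the first 100 subjects as the secondary test set, whichever look the primary passes at, and describe later subjects only. This keeps 2.5% and the stated n=100 power. The cost is that up to half the cohort is left out of the secondary tests when the primary passes only at the final look.
- **(b)** Give the secondaries their own two-look boundary, for example Pocock at one-sided 0.0147 at each look, and restate the n=100 power in 2.4.2.2 (83% to about 77%, 90% to about 86%).

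If 2.5.2 already sets secondary levels by look, cross-refer to it from 2.11.2 and reconcile the n=100 power statements with those levels. In each case, amend the type I error sentence in 2.11 to name the mechanism that gives control, and state in 2.6.2 which subjects the secondaries use when the primary passes only at the final look. These are SAP wording changes; visits, procedures and enrollment are unaffected.

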2.11.1 Multiplicity – Randomized Cohort

The secondary endpoints for the Randomized Cohort will be evaluated for labeling claims if the primary endpoint is met. The secondary endpoints for the Randomized Cohort will be tested sequentially in the following order:

- Freedom from major adverse events (MAE) occurring after procedure attempt (femoral vein puncture) at 30 days.
- Change in KCCQ at 12 months over baseline (superiority of Device vs. Control)
- TR Reduction to moderate or less at 30 days post procedure (superiority of Device vs. Control)
- Change in 6MWT at 12 months over baseline (superiority of Device vs. Control)
- Recurrent HF hospitalizations at 24 months (superiority of Device vs. Control)
- Freedom from all-cause mortality, tricuspid valve surgery, and tricuspid valve intervention at 24 months (superiority of Device vs. Control)

The two secondary endpoints assessed at 24 months (recurrent HF hospitalizations and freedom from all-cause mortality, tricuspid valve surgery and tricuspid valve intervention) will be evaluated when all randomized subjects complete 24-month follow-up for additional labeling claims.

2.11.2 Multiplicity – Single-Arm Cohort

The secondary endpoints for the Single-Arm Cohort will be evaluated for labeling claims if the primary endpoint of the Single-Arm Cohort is met. The secondary endpoints for the Single-Arm Cohort will be tested sequentially in the following order:

- TR Reduction by at least one grade at 30-day post procedure as compared to baseline.
- Freedom from major adverse events (MAE) occurring after procedure attempt (femoral vein puncture) at 30 days.
- Change in 6MWT at 12 months, as compared to baseline
- Freedom from all-cause mortality and tricuspid valve surgery at 12 months
- Recurrent HF Hospitalizations at 12 Months

Statistical Analysis Plan

2.12 Sensitivity Analysis

[REDACTED]

[REDACTED]

[REDACTED]

[REDACTED]

- [REDACTED]
- [REDACTED]
- [REDACTED]
- [REDACTED]

[REDACTED]

[REDACTED]

[REDACTED]

[REDACTED]

[REDACTED]

- [REDACTED]
- [REDACTED]
- [REDACTED]
- [REDACTED]
- [REDACTED]
- [REDACTED]

- [REDACTED]
- [REDACTED]
- [REDACTED]
- [REDACTED]
- [REDACTED]

Statistical Analysis Plan

[REDACTED]

[REDACTED]

[REDACTED]

[REDACTED]

[REDACTED]

[REDACTED]

[REDACTED]

[REDACTED]

[REDACTED]

[REDACTED]

[REDACTED]

[REDACTED]

[REDACTED]

[REDACTED]

[REDACTED]

Statistical Analysis Plan

[REDACTED]

2.12.2 Primary Endpoint for the Randomized Cohort Evaluated in All Randomized Subjects

A sensitivity analysis for the primary endpoint of the Randomized cohort will be performed based on all the randomized subjects. The same hypothesis test and statistical method will be implemented as specified in Section 2.3.1.1.

2.12.3 COVID-19 Relatedness

To understand the impact of COVID-19 pandemic on the clinical outcomes, sensitivity analysis for the primary endpoint of the randomized and single-arm will be performed to include all the adjudicated events and follow-up periods for each endpoint regardless the status of COVID-19 infection.

3.0 DESCRIPTIVE ENDPOINTS AND ADDITIONAL DATA

All endpoints in this section will be reported with descriptive statistics. Continuous endpoints will be summarized using the following: mean, standard deviation, median, the first and third quartiles, range, and the 95% confidence interval for the population mean using the normal approximation, when specified. Categorical endpoints will be summarized as proportions in the form of fractions and percentages. The 95% confidence interval for a population proportion will be constructed using the Clopper-Pearson exact method¹. The 95% confidence interval for the difference of two proportions will be constructed using the Newcombe² score method. Other analyses are specified under each category of additional descriptive endpoints.

3.1 Baseline and Demographic Characteristics

The following baseline and demographic variables will be summarized for the subjects enrolled: gender, age, ethnicity, race, medical history, baseline echocardiographic measurements, etc.

3.2 Adverse Events

All adverse device effects, serious adverse device effects, UADEs, and USADEs will be summarized for all enrolled subjects in terms of the number of events, the percentage of subjects with events per MedDRA coding. Procedure related AEs may also be summarized.

Statistical Analysis Plan

All CEC adjudicated adverse events will be summarized for all subjects who enrolled in the trial by treatment group in terms of the number of events, and the percentage of subjects with events. Moreover, COVID-19 related AEs will be summarized in terms of number of events, the percentage of subjects with events per AE term.

3.3 Subject Early Termination

Subject early termination reasons including death, withdrawal, lost-to-follow-up, etc. will be summarized by treatment group at all scheduled visits.

3.4 Protocol Deviation

Protocol deviations will be summarized for subjects with reported protocol deviations in the Randomized cohort, Single-arm cohort and Roll-In cohort separately. COVID-19 related protocol deviations will also be summarized.

3.5 Descriptive Endpoints

The descriptive endpoints for the Randomized Cohort will be summarized with descriptive statistics for the Device and Control groups respectively.

The descriptive endpoints for the Single-arm cohort will be summarized with descriptive statistics.

4.0 DOCUMENTATION AND OTHER CONSIDERATIONS

All analyses will be performed using SAS[®] for Windows, version 9.2 or higher.

Statistical Analysis Plan

5.0 ACRONYMS AND ABBREVIATIONS

Acronym or Abbreviation	Complete Phrase or Definition
6MWT	Six Minute Walk Test
CAS	Continued Access Study
CEC	Clinical Events Committee
CIP	Clinical Investigation Plan
CMH	Cochran-Mantel-Haenszel
CRF	Case Report Form
COVID-19	2019 Novel Coronavirus
EC	Eligibility Committee
ECL	Echocardiography Core Laboratory
EROA	Effective Regurgitant Orifice Area
GDMT	Guideline Directed Medical Therapy
HF	Heart Failure
HR	Hazard Ratio
JFM	Joint Frailty Model
KCCQ	Kansas City Cardiomyopathy Questionnaire
MAE	Major Adverse Event
MRI	Cardiac Magnetic Resonance Imaging
CT	Computed Tomography
NT-pro BNP	N-terminal prohormone of Brian Natriuretic Peptide
NYHA	New York Heart Association
RVEDD	Right Ventricular End Diastolic Dimension
LVEDV	Left Ventricular End Diastolic Volume
LVEDV	Left Ventricular End Diastolic Volume
TAPSE	Tricuspid Annular Plane Systolic Excursion
SAE	Serious Adverse Event
SAP	Statistical Analysis Plan
TEE	Trans-Esophageal Echocardiogram
TR	Tricuspid Regurgitation

Statistical Analysis Plan

7.0 APPENDICES

APPENDIX A: POWER AND SAMPLE SIZE CALCULATIONS

The R and SAS code will be provided in a separate document.

Statistical Analysis Plan

APPENDIX B: STATISTICAL ANALYSIS PLAN FOR CONTINUED ACCESS STUDY

B.1 Study Design

The TriClip™ Continued Access Study (CAS) of the TRILUMINATE Pivotal trial will be initiated upon the completion of enrollment of both the randomized and single-arm cohorts. The objective of this CAS will be to ensure continued access to the TriClip™ G4 device for eligible patients, while also providing additional experience for operators and supplementary safety and effectiveness data on the TriClip™ G4 device.

All subjects enrolled into the CAS will receive the TriClip™ G4 device. Enrollment into the CAS will continue until up to 600 subjects are enrolled or commercial approval is received, whichever occurs first. All subjects enrolled in the CAS will be followed for 5 years.

The same independent Clinical Events Committee (CEC) and Data Monitoring Committee (DMC) used for the randomized-arm and single-arm cohorts will adjudicate events for the CAS including cause of death, HF hospitalization and components of major adverse events. The same echo core lab (ECL) will be used for screening and evaluation of echocardiographic endpoints.

B.2 Study Endpoints

The following endpoints will be assessed and reported for the CAS.

- Technical Success at exit from procedure room: Alive with successful access, delivery and retrieval of the device delivery system, and deployment and correct positioning of a Clip, and no need for additional unplanned or emergency surgery or re-intervention related to the device or access procedure
- Device Success at 30-day post-procedure: Alive with original intended Clip(s) in place, and no additional surgical or interventional procedures related to access or device since completion of the original procedure, and intended performance of the Clip(s) (i.e. ≥ 1 grade improvement in TR severity, no embolization, single leaflet device attachment, absence of para-device complications)
- Procedural Success at 30-day post-procedure: Device success, and no device or procedure related SAE
- TR Reduction by at least one grade at 30-day post procedure as compared to baseline.
- Freedom from MAE occurring after procedure attempt (femoral vein puncture) at 30 days.
Components of MAE consist of the following:
 - Cardiovascular Mortality,
 - New Onset Renal Failure,
 - Endocarditis Requiring Surgery, and
 - Non-Elective Cardiovascular Surgery for TriClip™ device-related AE post-index procedure.
- Recurrent HF hospitalizations at 12 months compared to the rate of heart failure hospitalizations in the prior 12 months
- Freedom from all-cause mortality and tricuspid valve surgery at 12 months

Statistical Analysis Plan

- Incidence of peripheral edema requiring hospitalization at 12 months, and annually through 24, 36, 48, and 60 months
- Incidence of ascites at 12 months, and annually through 24, 36, 48, and 60 months
- Incidence of IV diuretic administration (including outpatient clinics) at 12 months, and annually through 24, 36, 48, and 60 months
- Change in KCCQ score from baseline through 30 days, 12 months and annually through 24, 36, 48, and 60 months
- Change in NYHA Functional Class (III/IV to I/II) from baseline through 30 days 12 months and annually through 24, 36, 48, and 60 months
- Echocardiographic endpoints assessed from baseline through 30 days, 12 months and annually through 24, 36, 48, and 60 months post procedure, as follows:
 - TR severity grade
 - Tricuspid valve annulus diameter
 - Effective Regurgitant Orifice Area (EROA)
 - Regurgitant Volume
 - Cardiac Output
 - Forward Stroke Volume (Left Ventricle)

B.3 Analysis Consideration

B.3.1 Analysis Population

The analysis for the CAS will include all continued access subjects that receive treatment with the TriClip™ G4 device. The Attempted Procedure population will be used for the endpoint analysis for the continuous access study, which will consist of subjects in whom a TriClip™ G4 procedure is attempted, i.e., undergo femoral vein puncture.

B.3.2 Endpoints Analysis

All the analysis for the CAS endpoints will be descriptive. Continuous endpoints will be summarized using the following: mean, standard deviation, median, the first and third quartiles, range, and the 95% confidence interval for the population mean using the normal approximation, when specified. Categorical endpoints will be summarized as proportions in the form of fractions and percentages. The 95% confidence interval for a population proportion will be constructed using the Clopper-Pearson exact method¹. The 95% confidence interval for the difference of two proportions will be constructed using the Newcombe score method. Other analyses are specified under each category of additional descriptive endpoints. Survival analysis will be conducted to analyze time-to-event variables. Subjects without events will be censored at their last known event-free time point when they stay in the study. Survival curves will be constructed using Kaplan-Meier estimates.

Statistical Analysis Plan

B.3.3 Baseline and Demographic Characteristics

The following baseline and demographic variables will be summarized for the subjects enrolled: gender, age, ethnicity, race, medical history, baseline echocardiographic measurements, etc.

B.3.4 Adverse Events

All adverse device effects, serious adverse device effects, UADEs, and USADEs will be summarized for all enrolled subjects in terms of the number of events, the percentage of subjects with events per MedDRA coding. Procedure related AEs may also be summarized.

All CEC adjudicated adverse events will be summarized for all subjects who enrolled in the trial in terms of the number of events, and the percentage of subjects with events. Moreover, COVID-19 related AEs will be summarized in terms of number of events, the percentage of subjects with events per AE term.

B.3.5 Protocol Deviation

Protocol deviations will be summarized for subjects with reported protocol deviations. COVID-19 related protocol deviations will also be summarized.

Statistical Analysis Plan

